### **9.4 Study Restrictions**

#### **9.4.1 Prohibited Medications**

[Table 9-2](#) lists prohibited medications. A non-exhaustive list of study prohibitions and cautions for medication will be provided in the Study Reference Manual.

**Table 9-2 Prohibited Medications**

Medication	Timing of Restriction		Rationale
	Start of Restriction	End of Restriction	
Moderate and strong CYP3A inducers	None allowed within 14 days before the first dose of ELX/TEZ/IVA on Day -28	None allowed through completion of study participation	VX-121, ELX, TEZ, IVA, and D-IVA are metabolized extensively via CYP3A4. Therefore, use of moderate and strong inducers and inhibitors of CYP3A, which have the potential to alter the exposure of VX-121, ELX, TEZ, IVA, and D-IVA, will be prohibited.
Moderate and strong CYP3A inhibitors (except ciprofloxacin)			
Non-Vertex CFTR modulators (investigational or approved)	None allowed within 28 days or 5 terminal half-lives (whichever is longer) before screening	None allowed through completion of study participation	These agents may confound the results of this study.
Vertex CFTR modulators (investigational or approved), except for study drugs	None allowed from the first dose of ELX/TEZ/IVA on Day -28	None allowed until after the last dose of study drug	These agents may confound the results of this study.

D-IVA: deutivacaftor; ELX: elexacaftor; IVA: ivacaftor; TEZ: tezacaftor

## 9.5 Prior and Concomitant Medications

Information regarding prior and concomitant medications, including CF medications, other medications, and herbal and naturopathic remedies, will be collected from each subject's source documentation for medications taken within 56 days before the Screening Visit through completion of study participation, as defined in Section 9.1.7.

- Subjects should remain on a stable treatment regimen for their CF from 28 days before the Run-in/Day -28 through completion of study participation. Stable treatment regimen is defined as the current treatment regimen for CF that subjects have been following for at least 28 days before the Run-in/Day -28. Subjects may remain on Vertex CFTR modulators (investigational or approved) during the Screening Period and may transition directly to the Run-in/Day -28 without a washout (Table 9-2). Subjects should not initiate long-term treatment with new medication from 28 days before the Run-in/Day -28 through completion of study participation. Guidelines for stable treatment regimens for CF are as follows:
  - o Subjects who are taking inhaled tobramycin or other chronically inhaled antibiotics should remain on that regimen throughout the study.
  - o Subjects who cycle onto and off of an inhaled antibiotic should continue on their prior schedule. The timing of the first dose of ELX/TEZ/IVA in the Run-in Period should be synchronized as closely as possible (e.g., not more than  $\pm 3$  days) to the first day in the cycle onto the inhaled antibiotic.
  - o Subjects who alternate between 2 different inhaled antibiotics should remain on the same cycling schedule during the study. The timing of the first dose of ELX/TEZ/IVA in the Run-in Period should be synchronized as closely as possible

(e.g., not more than  $\pm 3$  days) to the first day in the cycle onto 1 of the inhaled antibiotics.

- Subjects may receive doses of prednisone or prednisolone of up to 10 mg/day chronically. Subjects cannot receive prednisone or prednisolone at doses  $>60$  mg qd for longer than a 5-day period.
- TEZ/IVA is a weak inhibitor of OATP1B1, and ELX and M23-ELX are potential inhibitors of OATP1B1 and OATP1B3. Administration of VX-121/TEZ/D-IVA or ELX/TEZ/IVA may increase systemic exposure of substrates of OATP1B1/1B3, which may increase or prolong their therapeutic effect and adverse reactions; therefore, caution and appropriate monitoring should be used when coadministration of study drugs with medicinal products that are substrates of OATP1B1/1B3, such as statins, glyburide, nateglinide, and repaglinide, is required.
- IVA and D-IVA are weak inhibitors of P-glycoprotein (P-gp). Administration of IVA or D-IVA may increase systemic exposure of medicinal products that are sensitive substrates of P-gp, which may increase or prolong their therapeutic effect and adverse reactions. Digoxin or other substrates of P-gp with a narrow therapeutic index, such as cyclosporine, everolimus, sirolimus, and tacrolimus, should be used with caution and appropriate monitoring.
- IVA and D-IVA may inhibit CYP2C9; therefore, during coadministration with warfarin, additional monitoring of the international normalized ratio is recommended. Other medicinal products that are CYP2C9 substrates for which exposure may be increased include glimepiride and glipizide; these should be used with caution.
- Subjects who are using a bronchodilator must have their spirometry assessments performed according to the guidelines provided in Section 11.5.1.

## 9.6 Administration

### 9.6.1 Dosing

Study drug will be administered orally. All subjects will receive the same number of tablets each day to maintain the blind. Additional information is provided in the Pharmacy Manual.

Study drug will be administered with a fat-containing meal or snack, such as a standard “CF” meal or snack or a standard meal.

1. It is recommended that the dose be taken within 30 minutes of the start of the meal or snack.
2. Study drug will be administered as FDC tablets (e.g., 2 VX-121/TEZ/D-IVA or matching placebo tablets; 2 ELX/TEZ/IVA or matching placebo tablets) in the morning and as 1 IVA or matching placebo tablet in the evening. For each subject, doses of study drugs will be taken at approximately the same time ( $\pm 2$  hours) each day.
3. The date, amount taken, and time of study drug administration, including whether food was taken with each dose, will be recorded for the 2 doses before PK sample collection and the dose received on the morning of PK sample collection.
4. On days of scheduled visits, the morning dose of study drug will be administered at the site after predose assessments have been completed. A meal or snack will be provided by the site for the morning dose of study drug.

5. If a subject's scheduled visit is to occur in the afternoon, the following guidelines must be used:
  - If the dose in the clinic will be within 6 hours of the subject's scheduled morning dose, the subject should withhold their morning dose of study drug and the morning dose will be administered in the clinic.
  - If the dose in the clinic will be more than 6 hours after the subject's scheduled morning dose, the subject should take the morning dose of study drug at home.
  - At the Day 1 Visit, the morning dose of study drug must be administered in the clinic to enable predose and/or postdose PK sampling relative to the morning dose.
6. Subjects will be instructed to bring all used and unused materials associated with the study drug to the site; study drug will be dispensed at each visit, as appropriate.

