**Table 3-2 Study VX20-121-103: Run-in Period, Treatment Period, and Safety Follow-up Visit**

Event/Assessment a	Run-in Period		Treatment Period b						ETT Visit c	Safety Follow-up Visit 28 (± 7) Days After the Last Dose of Study Drug (If Applicable) d	Comments
	Day -28 (± 1 Day)	Day -14 (Day -15 to Day -3)	Day 1	Day 15 (± 3 Days)	Weeks 4, 8, 12, 16 (± 5 Days)	Weeks 20, 28, 32, 40, 44, 48 (± 5 Days)	Weeks 24 and 36 (± 5 Days)	Week 52 (± 5 Days)			
Pulse oximetry	X		X	X	X		X	X	X	X	After the subject has been at rest for at least 5 minutes, and before dosing (as applicable) (Section 11.6.4)
Spirometry (in-clinic)		X	X	X	Weeks 4, 8, 16		X	X	X	X	Should be performed pre-bronchodilator, before dosing, and at approximately the same time at each visit. If the visit is performed as a home health visit, spirometry may be performed using a mobile device (Section 9.1.8).
Spirometry (mobile device)		X	X								Spirometry with a mobile device should be performed at home and as applicable (Section 9.1.8)
Sweat chloride		X	X	X	Weeks 4 and 16		X	X	X		Will be performed before dosing (Section 11.5.2)
Serum chemistry	X		X g	X	X		X	X	X	X	Section 11.6.2
Hematology	X		X g	X	X		X	X	X	X	Section 11.6.2
HbA1c			X g		Week 12		Week 24	X			HbA1c will be collected as part of the hematology blood draw (Section 11.6.2)
Coagulation	X		X g		Week 12		X	X	X	X	Section 11.6.2
Urinalysis	X		X		Week 12		X	X	X	X	Section 11.6.2
PK sampling			Predose and 2 hours postdose	Predose	Weeks 4, 8, 16: predose		Week 24: predose		X		Refer to Table 11-1 for acceptable PK sampling windows. At the ETT Visit, a single PK blood sample will be collected.
DNA sample (optional)			X								If permitted by local regulations (Section 11.4.1)
Inflammatory mediator samples	X		X		Week 4		Week 24	X			Section 11.4.2
Blood sample for RNA (optional)	X		X		Week 4		Week 24	X			If permitted by local regulations (Section 11.4.3)
Blood biomarker samples	X		X		Week 4		Week 24	X			Section 11.4.3

g Blood samples will be collected before the first dose of study drug in the Treatment Period.

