### 11.2 Pharmacokinetics

#### 11.2.1 Blood Sampling

Blood samples will be collected to determine plasma concentrations of VX-121, TEZ, D-IVA, ELX, IVA, and relevant metabolites. These samples may also be used for further evaluation of the bioanalytical method, or for exploratory analyses that provide information on the metabolic pathways used by or affected by any study drugs.

All efforts will be made to obtain the PK samples at the exact nominal time relative to dosing. Acceptable windows for sampling times are shown in Table 11-1. Samples collected outside of these acceptable windows will be considered protocol deviations. The exact time of the sample collection will be noted.

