## 11.5 Efficacy

### 11.5.1 Spirometry

Spirometry will be performed according to the American Thoracic Society Guidelines/European Respiratory Society Guidelines and according to the additional guidelines that follow.

Pre-bronchodilator spirometry is defined as spirometry testing performed for subjects who have

- withheld their short-acting bronchodilators (e.g., albuterol) or anticholinergic (e.g., ipratropium bromide [Atrovent®]) for more than 4 hours before the spirometry assessment;
- withheld their long-acting bronchodilator (e.g., salmeterol) for more than 12 hours before the spirometry assessment; and
- withheld their once-daily, long-acting bronchodilator (e.g., tiotropium bromide [Spiriva®]) for more than 24 hours before the spirometry assessment.

During the Screening Period, spirometry assessments may be performed pre- or post-bronchodilator. At all other visits, all spirometry assessments should be performed pre-bronchodilator. During the Treatment Period, spirometry assessments must be performed before study drug dosing (Section 9.6.1) at approximately the same time at each visit. In the event that a subject forgets to withhold bronchodilator(s), spirometry should be performed according to the following:

- If a subject's Day 1 spirometry assessment is pre-bronchodilator, but, on a subsequent visit, the subject forgets to withhold bronchodilator use, a post-bronchodilator spirometry assessment will be obtained for that visit only, and the visit will not be rescheduled.
- If, on Day 1, the subject forgets to withhold his/her dose of bronchodilator, spirometry should be performed post-bronchodilator, and all subsequent spirometric measurements (according to the schedule of assessments in Table 3-2) should be performed post-bronchodilator.
- Each spirometry assessment will be recorded in the source documents as pre- or post-bronchodilator.

Spirometers will be provided to be used for all study assessments. During study visits, spirometry assessments will be conducted per Table 3-1 and Table 3-2 and will be performed on more than one spirometer as applicable. All spirometry data will be transmitted to a centralized spirometry service for quality review. The investigator's assessment of the spirometry results will be used for the screening assessment and determination of eligibility.

See Section 10.7.1 for information about access to spirometry results.

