### **11.5.2 Sweat Chloride**

SwCl samples will be collected with an approved collection device. Each collection will occur before study drug dosing (Section 9.6.1). At each time point, 2 samples will be collected, 1 from each arm (left and right). Sweat samples will be sent to a central laboratory for testing and interpretation of results. Specific instructions for the collection, handling, processing, and shipping of SwCl samples to the central laboratory will be provided separately.

See Section 10.7.1 for information about access to SwCl results.

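### At late-afternoon visits after Day 1, the home-dosing rule in Protocol 9.6.1 conflicts with the predose rules for spirometry, sweat chloride and PK

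*Protocol*

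**What the plan says.** Protocol 9.6.1 contains a general visit-day rule and a rule for afternoon visits.

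- Item 4, general: "On days of scheduled visits, the morning dose of study drug will be administered at the site after predose assessments have been completed".
- Item 5, afternoon visits, introduced as mandatory: if the clinic dose would fall within 6 hours of the usual morning dose, the subject waits and is dosed in clinic. If it would fall "more than 6 hours after the subject's scheduled morning dose, the subject should take the morning dose of study drug at home".
- The only carve-out in item 5: "At the Day 1 Visit, the morning dose of study drug must be administered in the clinic". The reason given is to allow PK sampling relative to that dose.

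The assessment sections are written without condition.

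- Section 11.5.1: "During the Treatment Period, spirometry assessments must be performed before study drug dosing". The sentence goes on to require roughly the same time at each visit.
- Section 11.5.2: "Each collection will occur before study drug dosing".
- Table 3-2, PK row: predose at Day 15, then "Weeks 4, 8, 16: predose", and predose again at Week 24.
- Table 11-1 sets the predose window at 60 minutes before dosing, and 11.2.1 adds: "Samples collected outside of these acceptable windows will be considered protocol deviations".

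SAP 8.3.1.1 estimates the primary variable by averaging Weeks 16 and 24. SAP 8.1 takes the predose Day 1 value as efficacy baseline. For sweat chloride it averages the two most recent predose values from Day -14 onward.

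**The concern.** A subject sent to clinic already dosed cannot give a predose measurement for that morning's dose. Item 5 therefore directs the site to do something that 11.5.1, 11.5.2 and the PK row of Table 3-2 rule out. The Day 1 carve-out shows that the authors saw that home dosing defeats PK sampling around the dose, but they protected only that visit. Weeks 16 and 24, which carry the primary and key secondary estimates, are left open.

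Three things are at stake. First, a postdose Week 16 or 24 value set against a predose Day 1 value mixes different times since dosing within one subject. Second, a sweat chloride value close to 30 or 60 mmol/L could change responder status. Third, a site that obeys the dosing section produces a PK protocol deviation. The SAP has dose-timing rules for baseline only (8.1, and Appendix A note 3 and derived variable 4). It has no rule for post-baseline values taken after that day's dose.

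**Working it through.** **1. Timing at one visit.** The clock times are an illustration. Take a usual dose at 08:00 and a clinic dose slot at 15:00.

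- Delay = 15:00 − 08:00 = 7 hours, which exceeds 6, so item 5 sends the dose home.
- Assessments just before 15:00 are then about 7 hours postdose.
- Item 2 says that "doses of study drugs will be taken at approximately the same time", within 2 hours either way. A home dose at 10:00 gives 15:00 − 10:00 = 5 hours.

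Roughly 6 hours or more is therefore the fair description; more than 6 hours is not a strict minimum. In either case the PK sample misses the predose window.

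**2. Which visits are exposed, and where dose time is already captured.** Item 3 of 9.6.1 records the time of the two doses before each PK sample and of the dose taken that morning. Set against Table 3-2:

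| Visit | Spirometry | Sweat chloride | Predose PK | Dose time recorded |
|---|---|---|---|---|
| Day 15, Week 4 | yes | yes | yes | yes |
| Week 8 | yes | no | yes | yes |
| Weeks 16, 24 | yes | yes | yes | yes |
| Weeks 36, 52 | yes | yes | no | no |

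Every visit in the primary model (SAP 8.3.1.3) and the sweat chloride model (SAP 8.3.2.2) already has a dose time. Only Weeks 36 and 52 lack one. At Week 52, Table 3-2 ends dosing the evening before, so no morning dose should arise there.

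**3. The plan's own power figures.** Protocol 12.1 gives 275 per group, 10% dropout, and SDs of 8 points and 14 mmol/L. Evaluable per group = 275 × 0.9 = 247.5, taken as 247. Normal approximation:

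- Primary: SE = 8 × √(2/247) = 0.720. Power = Φ(3/0.720 − 1.96) = 98.6%, against the stated more than 95%.
- Sweat chloride: SE = 14 × √(2/247) = 1.260. Power = Φ(5/1.260 − 1.96) = 97.8%, against the stated more than 95%.

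Both figures reproduce. The conflict changes none of them.

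**4. Illustrative size.** Let f be the share of Week 16/24 values taken postdose and s the between-arm difference in postdose shift. The treatment difference moves by f × s. The documents give neither quantity, so both are assumptions.

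| f | s | Movement | Primary power if adverse |
|---|---|---|---|
| 5% | 1 point | 0.05 | 98.4% |
| 10% | 2 points | 0.20 | 97.3% |
| 20% | 2 points | 0.40 | 95.1% |
| 30% | 3 points | 0.90 | 83.1% |

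For sweat chloride, with f of 5% to 10% and s of 2 to 4 mmol/L, the movement is 0.05 × 2 = 0.1 to 0.10 × 4 = 0.4 mmol/L against the planned 5. The sign is unknown in every row: a movement in favour of the new regimen would make non-inferiority easier to show by the same amount.

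**The case against.** **Item 5 is the noted exception.** Section 3 and footnote a of Table 3-2 require predose assessments unless noted otherwise, and 11.5.1 and 11.5.2 both cross-refer to 9.6.1. This is arguable for efficacy but weak. Where the protocol wants conditional timing it says so: pulse oximetry (11.6.4) is predose at visits where drug is taken at the site, and vital signs and ECG (11.6.3, 11.6.5) are predose as applicable. Spirometry, sweat chloride and PK carry no such words. For PK the argument fails, because the sample taken under item 5 is a deviation by 11.2.1.

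**The same-time rule already prevents it.** It probably reduces the number of cases but does not remove them. A subject whose Day 1 visit is at 15:00 is dosed in clinic and has a predose baseline. At Week 16, again at 15:00, item 5 sends the same subject in already dosed. The clock time matches and the time since dosing does not.

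**The effect is small and applies to both blinded arms.** This largely stands. One rule governs both arms, and no postdose shift is documented for either.

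**PK is not lost.** This also stands. Exact dose and sample times are recorded, and Protocol 12.6.1 allows nonlinear mixed-effects modelling, which can use actual times. The sample is a deviation and not a trough, but it may still be usable.

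A reader might also see a contradiction between the 2-hour tolerance in item 2 and the 6-hour limit in item 5. The documents do not support that: item 2 is the everyday rule and item 5 a specific visit-day exception to it.

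**Conclusion.** The conflict is real and can be read directly from the text. At late-afternoon visits other than Day 1, a site cannot meet item 5 together with item 4, 11.5.1, 11.5.2 and the PK row of Table 3-2. The supported consequences are a within-subject timing mismatch against a predose Day 1 baseline, some added variability, and PK deviations that the protocol itself creates. For sweat chloride the mismatch is less clean, because the baseline also averages in a Day -14 value, a visit that item 5 does not protect.

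A reader might infer that the primary comparison is biased, since only the control arm has an active evening dose and the shifts need not cancel. That is possible but not shown. With 5% to 10% of values affected and a between-arm difference in shift of 1 to 2 points, the movement is 0.05 to 0.2 points against a margin of 3, and power stays at 97.3% or higher if it is adverse. Power falls clearly below the stated 95% only when a large share of affected visits is combined with a large difference in shift. The conflict is unlikely to overturn non-inferiority. Confidence is high for the textual conflict and low for any figure on its effect.

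**What to change.** **Protocol.** The sponsor must reconcile 9.6.1 item 5 with item 4, 11.5.1, 11.5.2 and Table 3-2. No dosing rule is proposed here. Scheduling visits with predose assessments so that the conflict does not arise is one option.

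**SAP.** Use the dose times already recorded under 9.6.1 item 3 to flag spirometry and sweat chloride values taken after that day's dose, from Day 15 through Week 24. Report the number flagged by arm and visit. Add one sensitivity analysis that repeats the primary and sweat chloride analyses with flagged Week 16 and 24 values set to missing. For the pooled responder endpoints this covers the Study 103 part; whether Study 102 holds the same dose times cannot be told from these documents.

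**Data collection.** Add a dose-time field at Weeks 36 and 52 only, for the endpoints through Week 52. At Week 52 it should mainly confirm that no dose was taken that morning.

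**Cost.** A protocol clarification, one field at two visits and one extra table. If the scheduling option is chosen, visit booking becomes slightly less flexible.

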### **9.6.2 Missed Doses**

If 6 hours or less have passed since the missed morning or evening dose, the subject should take the missed dose as soon as possible and continue on the original schedule.

**Morning dose:** If more than 6 hours have passed since the missed morning dose, the subject should take the missed dose as soon as possible and should not take the evening dose.

**Evening dose:** If more than 6 hours have passed since the missed evening dose, the subject should not take the missed dose. The next scheduled morning dose should be taken at the usual time.

Morning and evening doses should not be taken at the same time.

### **9.7 Dose Modification for Toxicity**

No dose modifications for toxicity are allowed. Treatment may be interrupted as outlined in Section 9.8. If any unacceptable toxicity arises, individual subjects will discontinue dosing (Section 9.9).

### **9.8 Study Drug Interruption and Stopping Rules**

The medical monitor should be notified of an interruption of study drug that lasts >72 hours for any reason and of the resumption of study drug after such interruption.

#### **9.8.1 Liver Function Tests**

The central laboratory will notify the medical monitor of ALT or AST  $>3 \times$  ULN and total bilirubin  $>2 \times$  ULN that are derived from centrally submitted samples.

Subjects with new treatment-emergent ALT or AST elevations of  $>3 \times$  ULN, with or without total bilirubin  $>2 \times$  ULN, must be followed closely, including confirmatory testing performed by the central laboratory within 48 to 72 hours of the initial finding and subsequent close monitoring of ALT, AST, and bilirubin levels, as clinically indicated.

If a subject cannot return to the site for confirmatory testing, a local laboratory may be used. Local laboratory results must be reported immediately to the medical monitor, and the subject

must have the tests repeated and sent to the central laboratory as soon as possible (ideally within 48 to 72 hours).

Study drug administration **must be interrupted** immediately (prior to confirmatory testing) if any of the following criteria are met:

- ALT or AST  $>8 \times$  ULN
- ALT or AST  $>5 \times$  ULN for more than 2 weeks
- ALT or AST  $>3 \times$  ULN, in association with total bilirubin  $>2 \times$  ULN and/or clinical jaundice

A thorough investigation of potential causes should be conducted, and the subject should be followed closely for clinical progression.

Study drug administration **must be discontinued** if the following criterion is met:

- Subsequent ALT or AST values confirm the initial elevation that satisfied the interruption rule (above), and no convincing alternative etiology (e.g., acetaminophen use, viral hepatitis, alcohol ingestion) is identified, regardless of whether transaminase levels have improved

All subjects in whom treatment is discontinued for elevated transaminases (and bilirubin, as applicable) should have these levels monitored closely until levels normalize or return to baseline.

If an alternative, reversible cause of transaminase elevation with or without increased bilirubin or clinical jaundice has been identified, study drug administration may be resumed once transaminases return to baseline or are  $\leq 2 \times$  ULN, whichever is higher. Regardless of the duration of interruption, the medical monitor should be notified prior to resumption of study drug. Upon resumption of study drug, transaminases and bilirubin should be assessed weekly for 4 weeks. If a protocol-defined transaminase elevation interruption threshold recurs within 4 weeks of rechallenge with the study drug (with confirmation of the initial elevation by repeat testing within 48 to 72 hours), then the study drug must be permanently discontinued, regardless of the presumed etiology.

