#### **8.4.2 Clinical Laboratory**

For the treatment-emergent laboratory assessments, the observed values and change from baseline values of the continuous hematology, coagulation, and chemistry results will be summarized in SI units at each visit by treatment group.

The number and percentage of subjects meeting at least 1 threshold analysis criterion event during the TE Period for the Treatment Period will be summarized by treatment group. The threshold analysis criterion shift from baseline will also be summarized for select laboratory parameters. The threshold analysis criteria are provided in [Appendix](#) .

For select liver function laboratory tests (alanine transaminase [ALT], aspartate transaminase [AST], alkaline phosphatase [ALP], and total bilirubin), a scatterplot of the maximum TE value versus the baseline value corresponding to xULN (upper limit of normal) will be presented. Further, a scatterplot of the maximum TE value of ALT and AST, separately, versus the maximum TE value of total bilirubin corresponding to xULN will also be presented by treatment group. For ALT, AST, and total bilirubin, box-and-whisker plots will be used to display raw values at each visit by treatment group.

Results of positive serum/urine pregnancy tests will be listed in individual subject data listings only. For the positive serum pregnancy listing, subjects with serum HCG which are abnormally high will be selected.

In addition, listings containing individual subject hematology, chemistry, coagulation, and urinalysis values will be provided. The listings will include data from both scheduled and unscheduled visits. A listing of subjects who meet the criteria of [(ALT>3xULN or AST>3xULN) and TBILI>2xULN] at any visit will be provided. This listing will include data from all visits (including unscheduled visits) and present values for ALT, AST, ALP, and total bilirubin.

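### After a liver event with raised bilirubin or jaundice, Protocol Section 9.8.1 allows restart once transaminases alone recover

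*Protocol*

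**What the plan says.** The rules are all in Protocol Section 9.8.1.

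- **Interruption.** Drug stops at once, before confirmatory testing, on any of three criteria: ALT or AST >8×ULN; ALT or AST >5×ULN for more than 2 weeks; or ALT or AST >3×ULN "in association with total bilirubin" >2×ULN and/or clinical jaundice. The third is called the combined event below.
- **Permanent discontinuation.** Treatment ends if later ALT or AST values confirm the elevation and no convincing other cause is found, even if transaminases have since improved.
- **Restart.** The rule opens: "If an alternative, reversible cause of transaminase elevation with or without increased bilirubin or clinical jaundice has been identified". Its recovery condition follows: "study drug administration may be resumed once transaminases return to baseline or are" ≤2×ULN, whichever is higher.
- **Before and after restart.** Whatever the length of the interruption, "the medical monitor should be notified prior to resumption of study drug". Afterwards, "transaminases and bilirubin should be assessed weekly for 4 weeks". If a transaminase interruption threshold is met again within 4 weeks and confirmed, drug is stopped permanently whatever the presumed cause.
- **Monitoring.** The central laboratory alerts the medical monitor to ALT or AST >3×ULN and total bilirubin >2×ULN. New elevations call for confirmatory testing and "subsequent close monitoring of ALT, AST, and bilirubin levels, as clinically indicated". After an interruption, "A thorough investigation of potential causes should be conducted, and the subject should be followed closely for clinical progression".

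**The concern.** The restart rule names raised bilirubin and jaundice when it says which events it covers, then leaves both out when it says what must recover. Half of the combined trigger has a numeric restart limit and the other half has none. A site that follows the text exactly may re-expose a subject who is still jaundiced, or whose bilirubin is still above the level that helped force the stop.

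Two further features of Section 9.8.1 bear on this. First, subjects who are permanently discontinued are to have transaminases, and bilirubin where applicable, monitored closely until they normalize or return to baseline. Bilirubin is thus followed to recovery in people who will not be re-exposed, but its recovery is not required in people who will be. Second, early restart can cost the subject the drug. While bilirubin stays >2×ULN or jaundice persists, ALT or AST need only pass 3×ULN to meet the third criterion again. Otherwise they must pass 8×ULN, or 5×ULN for more than 2 weeks. A confirmed recurrence within 4 weeks ends treatment.

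**Working it through.** The plan gives no figure to reproduce, so the check applies the written rules to example subjects. All values are multiples of ULN. ALT stands for the higher of ALT and AST. The example values are illustrative and do not come from the documents.

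**Rules**

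1. Interruption (Section 9.8.1): ALT >8; or ALT >5 for more than 2 weeks; or ALT >3 with bilirubin >2 or jaundice.
2. Current restart (Section 9.8.1, other reversible cause identified): ALT ≤ max(baseline ALT, 2).
3. Proposed restart: rule 2 holds, and bilirubin ≤ max(2, last pre-event bilirubin), and no jaundice, and rule 1 is not met.

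**Event.** ALT 4.0, bilirubin 2.5, jaundice present. Since 4.0 > 3 and 2.5 > 2, interruption is mandatory. A reversible cause other than study drug is then identified.

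**Possible states when restart is considered.** Baseline ALT is 0.8 and last pre-event bilirubin 1.0 unless stated. In A to E the current ALT limit is max(0.8, 2) = 2, and 1.8 ≤ 2 meets it.

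| State | ALT | Bilirubin | Jaundice | Current rule | Proposed rule |
|---|---|---|---|---|---|
| A | 1.8 | 2.5 | yes | restart | withhold: 2.5 > max(2, 1.0) = 2, and jaundice |
| B | 1.8 | 2.5 | no | restart | withhold: 2.5 > 2 |
| C | 1.8 | 1.8 | yes | restart | withhold: jaundice |
| D | 1.8 | 1.8 | no | restart | restart |
| E (pre-event bilirubin 2.3) | 1.8 | 2.3 | no | restart | restart: 2.3 ≤ max(2, 2.3) = 2.3 |
| F (baseline ALT 3.5) | 3.3 | 2.5 | no | restart: 3.3 ≤ max(3.5, 2) = 3.5 | withhold: 2.5 > 2, and rule 1 is met (3.3 > 3 with 2.5 > 2) |

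The current rule allows restart in all six states. In A, B and C the raised bilirubin, the jaundice or both remain. In F the restart rule and the interruption rule conflict: drug may resume while a criterion that requires stopping is met. If the last pre-event bilirubin in F had also been 2.5, the bilirubin clause would be met and only the no-criterion clause would withhold drug, which is why that clause is needed. F requires a baseline ALT above 3×ULN. Section 8.2 excludes ALT or AST ≥3×ULN at screening, so this needs a rise after screening and will be rare.

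**Is the missing condition supplied elsewhere?** Section 9.7 stops dosing for unacceptable toxicity but sets no restart limit. Section 9.8 asks that the medical monitor be told of interruptions over 72 hours and of resumption. Section 9.9 allows withdrawal from study drug for safety at the discretion of the investigator or sponsor. None states a bilirubin or jaundice condition for restart, and the SAP sets none.

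**The case against.** The strongest reply is that few subjects can reach this rule. A confirmed elevation without a convincing other cause ends treatment even if transaminases improve, so anyone considered for restart has an identified, reversible cause other than study drug. Resumption is permitted, not required. Causes must be investigated, the central laboratory alerts the medical monitor, the monitor is to be told again before restart, and weekly tests follow. Most investigators would probably wait for jaundice to clear.

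All of that stands, and it limits the size of the point. It does not supply the missing condition. Telling the medical monitor is not the same as needing approval, bilirubin monitoring is left to clinical indication, and the weekly tests begin only after re-exposure. The protocol chose a numeric limit for transaminases rather than leaving recovery to judgement.

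A second reply is that Section 9.8.1 is led by transaminases throughout. A subject on drug at ALT 1.8×ULN and bilirubin 2.5×ULN need not stop, so why withhold drug at the same values after an interruption? The two positions differ because the second subject has just had a mandatory stop to which bilirubin or jaundice contributed. It is still true that the exact bilirubin limit is a clinical judgement: neither document sets one for restart.

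A reader might go further and infer that the protocol allows rechallenge after unexplained or suspected drug-induced liver injury. The text does not support that: confirmed events of that kind are permanently discontinued.

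**Conclusion.** The point holds in a narrow form. After a combined event with an identified, reversible other cause, Section 9.8.1 permits rechallenge while total bilirubin is still >2×ULN or jaundice persists, and nothing else in the protocol or SAP prevents it. This follows from the wording and needs no assumption about data.

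Its size is small. The documents give no frequency. Affected subjects must have had the combined event, have another identified cause, and have bilirubin or jaundice that outlasts the transaminase rise. The point concerns the safety of those subjects and has no shown effect on the efficacy analyses. It does not follow that bilirubin alone should stop drug, or that restart is automatic. The change is worth making because it is cheap and the event is one that the protocol itself treats as needing an immediate stop.

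**What to change.** Add one sentence to the restart paragraph of Section 9.8.1, for example: where raised total bilirubin or clinical jaundice was part of the event, study drug may be resumed only when, in addition to the transaminase condition, total bilirubin is ≤2×ULN or back to the subject's baseline (the last value before the event), whichever is higher; clinical jaundice has resolved; and no interruption criterion in this section is currently met.

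The cost is one sentence in a protocol amendment or clarification letter. No new test is needed, because total bilirubin is in the same serum chemistry panel as ALT and AST (Table 11-2). The 2×ULN limit is the one already in the third interruption criterion. The bilirubin reference value is new to this section, so the sentence defines it. Allowing return to that value avoids barring a subject whose bilirubin was already above 2×ULN before the event.

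The downside is that some interruptions will last longer in a few subjects.
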